4.7.1. Adverse Events and Serious Adverse Events

The definitions for AEs and serious adverse events (SAEs) are described in Sections 7.1.1 and 7.1.2 of the study protocol, respectively. Additional information on determining whether abnormal laboratory or vital sign results should be considered as AEs is included in Section 7.2.6 of the study protocol. AEs and SAEs will be collected from the time of informed consent signature and then at each visit until the end of the study.

The severity of AEs is graded using 1 of 2 severity scales. The severity scale used is determined by the type of AE experienced by the subject; more detail is provided in Section 7.3.1 of the protocol.

Adverse Event Observation Period

- Pre-treatment AEs are AEs that developed or worsened or became serious during the pre-treatment period.
- Treatment-emergent AEs (TEAEs) are defined as AEs that are not present at baseline or represent the exacerbation of a preexisting condition during the SAFETY TREATMENT period (TEAE period). Therefore, referencing the protocol, TEAEs will be defined programmatically as any AE record with a start date/time on or after the first study drug administration (greater than or equal to study day 1), inclusive to the end of the TEAE period.
- Post-treatment AEs are AEs that developed or worsened or became serious during the POST-TREATMENT period.

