When the parent(s) or guardian(s) takes their child for medical attention for an acute respiratory infection, they will be instructed to take a Medical Information Packet with them for the treating clinician. For emergency and other visits to a medical facility other than the study site, medical records will be obtained by the investigator to gather information about treatments provided and use of concomitant medications or products.

It is recommended that site personnel contact the parent(s) or legal guardian(s) weekly between routine study visits, to obtain information about medically attended acute respiratory events and to remind the parent(s) or legal guardian(s) about the next scheduled study visit. Parent(s) or guardian(s) will be instructed to contact study personnel to report any abnormalities, including any hospitalizations or doctor visits, during the intervals between study visits and to come to the study site if medical evaluation is needed and the urgency of the situation permits. The follow-up period for the occurrence of RSV-confirmed medical attention will continue throughDay150.Safety,laboratory,andotherclinicalassessmentswillbe

	performed at specified study visits, until end of study, as noted.
Study Duration	Part A
	This is a single dose study with a treatment and follow-up duration of 150 days from baseline. The total duration of study will be up to 164 days (14-day screening period, single dose, and 150-day follow-up period).
	Part B:
	This is a repeat dose study with a treatment and follow-up duration of 237 days. The total duration of study will be up to 265 days (28-day screening period, 57-day treatment period, and 180-day follow-up period).
Sample Size:	Part A: Approximately 24 infants will be enrolled
	Part B: Approximately 1515 infants will be enrolled
Target Population:	The study population will consist of healthy male and female infants who have a chronological age of $\leq 6$ months at the time of first dose (ie, dosing on or before the subject's 6-month birthday), who have a GA no more than 35 weeks, 6 days, and who are not eligible, recommended for, nor have access to palivizumab by standard practice, local guidelines, or their healthcare provider.
Treatments	

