#### 9.5.3.3. Adverse Events

#### **Definitions**

For safety variables in Part A, 2 observation periods are defined:

- The pre-treatment period is defined as the time from signing the ICF to before the first dose of study drug.
- The treatment period is defined as the days from the first dose of study drug to the Day 150 visit.

Treatment-emergent AEs in Part A are defined as those that are not present at baseline or represent the exacerbation of a preexisting condition during the treatment period.

For safety variables in Part B, 3 observation periods are defined:

- The pre-treatment period is defined as the time from signing the ICF to before the first dose of study drug.
- The safety treatment period is defined as the time from the first dose of study drug up to the day of the last dose of study drug + 180 days.
- The post-treatment period: defined as starting the day after the end of the TEAE period.

Treatment-emergent adverse event in Part B are defined as those that are not present at baseline or represent the exacerbation of a pre-existing condition during the safety treatment period (TEAE period).

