5.8.1. Adverse Events

The verbatim text, the PT, and the primary SOC will be listed in subject listings. Summaries that include frequencies and proportions of subjects reporting AEs will include the PTs and the SOCs as appropriate.

The focus of adverse event reporting in the clinical study report will be on TEAEs. Pre-treatment and post-treatment AEs will be provided separately.

If an AE date/time of onset (occurrence, worsening, or becoming serious) is incomplete, an imputation algorithm will be used to classify the AE as pre-treatment, treatment-emergent, or post-treatment. The algorithm for imputing date/time of onset will be conservative and will classify an AE as treatment-emergent unless there is definitive information to determine pre-treatment status. For details on handling missing data and partial dates, see Section 6.3.

Summaries of all TEAEs in each treatment group will include:

- Overview of TEAEs, summarizing number and percentage of subjects with any
 - TEAEs.
 - Serious TEAEs.
 - TEAEs leading to death.
 - TEAEs leading to permanent treatment discontinuation.
 - TEAEs with severity of 3/4/5/Severe/Life-Threatening/Fatal (if multiple occurrences of an event for a subject, then worst severity is counted).
 - TEAEs that occurred within 2 days after either the first dose or the second dose (ie, post dose TEAE start date - dosing date \leq 2).
- All TEAEs by SOC and PT.
- All TEAEs by SOC, PT, and severity.
- All TEAEs by SOC, PT, and relationship (related, not related) to study drug.
- All TEAEs by SOC, PT, and relationship (related, not related) to injection procedure.
- TEAEs reported by \geq 5% of subjects in any treatment group by PT ordered by decreasing subject frequency in the combined REGN2222 group.
- TEAEs reported by \geq 1% of subjects in any treatment group by PT ordered by decreasing subject frequency in the combined REGN2222 group.
- Study drug-related TEAEs by SOC and PT.
- Study drug-related TEAEs by SOC, PT, and severity.
- Injection procedure-related TEAEs by SOC and PT.
- Injection procedure-related TEAEs by SOC, PT, and severity.

- Serious adverse events: All, study drug-related, and injection procedure-related TEAEs by SOC and PT.
- Death: All, study drug-related, and injection procedure-related TEAEs by SOC and PT. TEAEs leading to death are TEAEs that led to death regardless of timing of death in relation to study drug injection (ie, death occurring in the TEAE period or during the post-treatment period)

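### The SAP's start-date rule for TEAEs omits the exacerbation limb of its own definition, so a screening AE that worsens or turns serious after dosing on the same record is missed by the TEAE-based safety tables

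*SAP*

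**What the plan says.** SAP 4.7.1 states the concept first. TEAEs are "AEs that are not present at baseline or represent the exacerbation of a preexisting condition during the SAFETY TREATMENT period". Protocol 9.5.3.3 has the same concept for Part B: "those that are not present at baseline or represent the exacerbation of a pre-existing condition during the safety treatment period (TEAE period"). Neither sentence limits the exacerbation limb by the date on which the underlying event began.

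The next sentence of SAP 4.7.1 turns the concept into a rule, introduced as a consequence of it: "TEAEs will be defined programmatically as any AE record with a start date/time on or after the first study drug administration", up to the end of the TEAE period.

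The bullets on either side of the TEAE bullet are worded differently. Before dosing: "Pre-treatment AEs are AEs that developed or worsened or became serious during the pre-treatment period". After the TEAE period: "Post-treatment AEs are AEs that developed or worsened or became serious during the POST-TREATMENT period".

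Collection begins well before dosing: "AEs and SAEs will be collected from the time of informed consent signature". The Protocol synopsis divides Part B into a "28-day screening period, 57-day treatment period, and 180-day follow-up period".

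In SAP 5.8.1 the summaries of serious events, deaths, events of severity 3 or higher and events leading to discontinuation all cover TEAEs only, as does the subject listing of serious events. Pre-treatment AEs are to be provided separately, and the listing of deaths carries no TEAE restriction. Protocol 9.5.3.3 asks for deaths, AESIs and other SAEs to be listed and summarized by treatment arm in Part B, also without that restriction. SAP 1.2.3 declares no modification from the protocol's statistical section.

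**The concern.** The programmed rule is narrower than the definition it is meant to implement. The definition has two limbs, new events and exacerbations, and a start-date condition implements only the first unless every exacerbation carries its own record and start date.

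The rest of the SAP suggests an oversight. Section 5.8.1 describes onset in these terms: "If an AE date/time of onset (occurrence, worsening, or becoming serious) is incomplete". Section 6.3 has a rule for missing dates of worsening and seriousness. The data cut-off rule in Section 8 refers to events that worsen or become serious. Section 5.8 treats a laboratory value or vital sign that was abnormal at baseline and worsened on treatment as treatment-emergent. Section 5.8.1 also promises a conservative classification that favours treatment-emergent status when dates are incomplete, whereas the start-date rule leans the other way for complete dates.

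At stake is the completeness of the main safety tables in an infant prophylaxis trial. A post-injection deterioration that meets the protocol's definition could be missing from the table where a reader would look for it.

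**Working it through.** There is no plan figure to reproduce, and the point turns on no sample size or event count. The one number involved is the screening span, which is consistent with the stated maximum study duration: 28 + 57 + 180 = 265 days. The check is to apply the start-date rule to each possible order of events.

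- (a) AE starts after first dose. It meets the rule and is captured.
- (b) Condition present before consent and held as medical history, worsening after dosing. Protocol 7.1.1 makes the worsening an AE, so its record should start after dosing. Captured.
- (c) AE starts between consent and first dose and worsens after dosing, with the worsening entered as a new record. Captured.
- (d) As (c), but kept as one record with its start date in screening. It meets the exacerbation limb of the definition and fails the rule. Not captured.
- (e) AE starts in screening and becomes serious or fatal after dosing on the same record. It fails the rule. Not captured.

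Tracing (d) and (e) through the outputs in SAP 5.8.1:

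- TEAE summaries by SOC and PT: absent.
- Summaries of SAEs, deaths, severity 3 or higher, and discontinuation: absent, because each is a subset of TEAEs. The death summary allows death at any time, but the event leading to it must still be a TEAE.
- Listing of serious TEAEs: absent.
- Separate pre-treatment AE output: present, because the event developed before dosing.
- Listing of deaths: present if fatal.

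The SAP sentences that mention worsening or becoming serious do not rescue these cases. Those in 5.8.1 and 6.3 apply only when a date is missing or partial, and the one in Section 8 concerns only the cut-off for the first-step analysis.

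The two halves of the gap rest on different text. For (d) the programmed rule contradicts the definition directly. For (e) becoming serious is not named in the TEAE definition of either document. That part rests on the neighbouring bullets of SAP 4.7.1, the description of onset in 5.8.1, and the unrestricted SAE and death summaries in Protocol 9.5.3.3.

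**The case against.** The strongest reply is that the rule works as written once Protocol 7.1.1 is read with it. SAP 4.7.1 adopts that definition, under which worsening of a pre-existing condition is itself an AE. Each worsening then has its own start date, and the start-date rule implements the exacerbation limb. This stands for medical-history conditions. It does not settle the case of an AE already on a screening record: Protocol 7.2.1 leaves recording procedures to the study manual, which is not among the documents, and nothing in the protocol or SAP requires a new record when such an AE worsens or becomes serious. The SAP's references to repeated occurrences of one event within a subject show that separate records are possible, not that they are required.

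Second, the events are moved and not lost. That is right for the pre-treatment output and the deaths listing, but not for the summaries or the serious-event listing.

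Third, few infants are likely to be affected. Entry is limited to infants healthy apart from prematurity, screening safety assessments must be normal, eligibility is confirmed again on Day 1, febrile infants are not dosed, and 28 days is a maximum. This also stands.

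Fourth, the rule is the same in every arm of a randomized, blinded trial, and the safety analysis is descriptive. Nothing in the documents shows bias between arms.

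Fifth, no CRF field that dates a change in severity or seriousness is described. The SAP's missing-date rules presuppose such dates but do not prove that they are collected, so the remedy needs an alternative.

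**Conclusion.** The concern holds in a limited form. The SAP's programmed TEAE rule contradicts its own definition and that of Protocol 9.5.3.3 for one class of event: an AE first recorded between consent and first dose that worsens after dosing on the same record. For such an AE that turns serious or fatal, the SAP's TEAE-only summaries also depart from the protocol's unrestricted SAE and death summaries, with no modification declared. The conclusion assumes that the study manual does not already require a new record for these changes.

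A reader might infer that any post-injection deterioration of an existing problem goes missing. The documents do not support that, because worsening of a medical-history condition should already carry a post-dose start date. A reader might also infer that an appreciable share of SAEs would vanish from the tables. That would need the proportion of infants with an AE ongoing at first dose, the proportion of those who worsen without a new record, and the SAE rate. The documents give none of these, so no count or percentage can be defended, and the entry criteria suggest a small number.

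The case for correction before lock is that an explicit rule is wrong on its face, serious events are the ones concerned, and the remedy is cheap.

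**What to change.** In SAP 4.7.1, define a TEAE as any AE record whose onset, worsening or becoming serious falls on or after first dose and within the TEAE period, and date its treatment-emergent onset at that change. This carries the description of onset in SAP 5.8.1 into the rule.

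If the dates of such changes are not captured, require instead that each post-dose worsening or change to serious of a screening AE be entered as a new record. State that convention in the SAP, and query every AE ongoing at Day 1 before lock.

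In SAP 5.8.1, add a summary by treatment arm of all SAEs and deaths occurring after first dose, regardless of TEAE status, in line with Protocol 9.5.3.3.

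The cost is a short SAP revision and a small amount of extra programming and data review. The second route also needs site queries, limited to infants with an AE ongoing at first dose.

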4.7.2. Adverse Events of Special Interest

Adverse events of special interest (AESI) are AEs (serious or non-serious) required to be monitored, documented, and managed in a pre-specified manner as described in the protocol Section 7.2.4.2. AESIs for this study are hypersensitivity reactions occurring within 48 hours after exposure to the study drug (including but not limited to urticaria, edema, respiratory distress, anaphylaxis, and allergic reactions). Such treatment-emergent AESI are identified by investigator using a tick box on the eCRF AE page.

Preferred Terms of Interest for Identification of Hypersensitivity

As part of the safety assessment, in addition to evaluation of treatment-emergent AEs that are considered to be AESI by the investigator, the following sets of pre-defined PTs of interest for identification of treatment-emergent hypersensitivity AEs will also be monitored and summarized:

1. Modified narrow Standard MedDRA Query (SMQ [N]) for “hypersensitivity”. The modification is to add PTs: pruritus, pruritus generalised, prurigo, flushing, erythema, generalised erythema, injection site erythema, rash papular, allergic oedema.
2. MedDRA query for all PTs under the high level term (HLT): injection site reactions.
3. Hypersensitivity PTs of interest per [Carbonell-Estrany X. 2010](#) as listed in Appendix 11.5.
4. Hypersensitivity PTs of interest per [Feltes TF 2011](#) as listed in Appendix 11.6.
5. Acute hypersensitivity reactions **that occur within 2 days after dosing**, classified in 2 categories, per [Shapiro 2010](#):
 - a. Urticarial Reactions which will be identified by search for PTs: urticaria, oedema; low level term (LLT): localized erythema.
 - b. Allergic Rash which will be identified by search for PTs: rash, dermatitis allergic, erythema annulare, erythema multiforme, rash maculo-papular. For AEs coded to the PT of rash, a manual review of their verbatims will be conducted to identify AEs that are acute rash.

4.7.3. Laboratory Safety Variables

Clinical laboratory tests include hematology and blood chemistry. Samples for laboratory testing will be collected at screening, a post-baseline visit according to assigned blood draw schedule (time points specified in the schedule of assessments [Appendix 11.2]), and at Visit 7 or at the time of ET if the subject discontinued prior to Visit 7.

Clinical laboratory values will be in standard international (SI) units, including associated normal ranges provided by the central laboratory, and grouped by function in summary tables. Conventional unit may be provided. There are no universally accepted normal ranges for preterm infants. Therefore, the ranges provided by the central laboratory are associated with full-term infants and consequently, the ranges are to be used with caution in interpretation of results.

Clinical laboratory tests are provided below, sub-grouped by function. Both actual test values and “change from baseline” values (defined as the post-baseline value minus the baseline value) will be used in central lab result summaries. Potentially clinically significant values (PCSV) ranges will be applied to central lab test values as applicable (see Appendix 11.4 for PCSV definitions).

Blood Chemistry

| Electrolytes | Liver function | Metabolism | Renal function |
|---------------------|-----------------------|------------------------|-----------------------|
| Sodium | AST | Total protein, serum | Blood Urea Nitrogen |
| Potassium | ALT | Glucose | Creatinine |
| Chloride | Alkaline phosphatase | Albumin | Uric acid |
| Carbon dioxide | Total bilirubin | Creatine phosphokinase | |
| Calcium | Indirect bilirubin | | |
| | Lactate dehydrogenase | | |

Hematology

| Red blood cells and platelets | White blood cells |
|--------------------------------------|--------------------------|
| Hemoglobin | White blood cells (WBCs) |
| Hematocrit | Neutrophils |
| Red blood cells (RBCs) | Lymphocytes |
| Red cell indices | Monocytes |
| Platelet count | Basophils |
| | Eosinophils |

4.7.4. Vital Signs

The following vital signs parameters will be collected at Visit 1 (screening visit), Visit 2 (baseline visit), Visit 3, Visit 4, Visit 5, Visit 6, and Visit 7 or at the time of ET. On the study drug dosing days, vital signs will be assessed prior to collection of blood sample, prior to injection of study drug, and at 1 hour [±10 minutes] after completion of the injection.

- Respiration rate (breaths/min)
- Pulse rate (beat/min)
- Systolic and diastolic blood pressures (mmHg). Blood pressure may be difficult to obtain in some infants because of size, therefore a systolic blood pressure alone can be recorded.
- Temperature (°C / °F)

Both actual values and “change from baseline” values (defined as the post-baseline value minus the baseline value) will be used in vital sign result summaries. Potentially clinically significant values (PCSV) ranges will be applied to vital sign values as applicable (see Appendix 11.4 for PCSV definitions).

4.7.5. Physical Examination Variables

Subjects will have a physical examination (including weight) at Visit 1 (screening visit), Visit 2 (baseline visit), Visit 3, Visit 4, Visit 5, and Visit 7 or at the time of ET. On study drug-dosing days, physical examinations will be conducted predose and again postdose (excluding weight) prior to discharge. The result for each body system is an outcome of normal or abnormal.

4.8. Pharmacokinetic Variables and Anti-Drug Antibody Variables (ADA)

4.8.1. Pharmacokinetic Variables

Drug concentration in serum through Day 150 visit will be reported.

4.8.2. Anti-Drug Antibody Variables

Antidrug antibody variables include status and titer as follows. If ADA collected at screening is missing, it will be considered as negative at baseline.

- Total subjects with negative ADA assay response at all time points analyzed.
- Pre-existing immunoreactivity - defined as either a baseline positive ADA assay response (assessed with the sample collected at screen visit) with all post-baseline ADA assay results negative, or a baseline positive assay response with all post-baseline ADA assay responses less than 4-fold over baseline titer levels.
- Treatment-emergent - defined as any post-baseline positive ADA assay response after the initiation of study drug when the baseline ADA result is negative or missing.
 - Treatment-emergent will be further characterized:
 - persistent - defined as consecutive positive responses over at least a 12-week period
 - indeterminate - defined as positive only at the last sample analyzed
 - transient - defined as not persistent or indeterminate
- Treatment-boosted - defined as any post-baseline positive ADA assay response that is greater than or equal to 4-fold over baseline titer level when baseline response is ADA positive in the ADA assay.
- Titer values
- Titer category
 - Low (titer <1000)
 - Moderate ($1000 \leq \text{titer} \leq 10000$)
 - High (titer >10000)

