- 8. If the adverse event is considered a hypersensitivity or anaphylaxis reaction, then the adverse event will be assessed at as outlined in Table 4.
- 9. If the adverse event is a hypersensitivity reaction that results in a rash, then a photo will be taken as part of the adverse event assessment (also see Table 4).
- 10. The subjects with Schedule M will have the following collected: hematology/chemistry samples at screening, Day 29, and Day 150/ET; PK samples at Day 29 and Day 150/ET; and ADA samples at screening, Day 29, and Day 150/ET.
- 11. The subjects with blood collection Schedule L will have the following collected: hematology/chemistry samples at screening, Day 57 (predose), and Day 150/ET; PK samples at Day 57 (predose) and Day 150/ET; and ADA samples at screening, Day 57 (predose), and Day 150/ET.
- 12. The subjects with blood collection Schedule K will have the following collected: hematology/chemistry samples at screening, Day 85, and Day 150/ET; PK samples at Day 85 and Day 150/ET; and ADA samples at screening, Day 85, and Day 150/ET.
- 13. The subjects with blood collection Schedule J will have the following collected: hematology/chemistry samples at screening, Day 113, and Day 150/ET; PK samples at Day 113 and Day 150/ET; and ADA samples at screening, Day 113, and Day 150/ET.
- 14. The subjects with blood collection Schedule I will have the following collected: hematology/chemistry samples at screening and Day 150/ET; PK samples at Day 150/ET; and ADA samples at screening and Day 150/ET.
- 15. After substudy consent, the cheek swab for DNA in the optional substudy can be obtained at any time during the study period, but preferably at baseline.
- 16. If the subject experiences a medically attended respiratory infection since the previous scheduled visit, then the parent(s) or guardian(s) will be asked to provide additional pharmacoeconomic information on the event.
- 17. Visits 8, 9, and 10 will be done by telephone contact. In the event an AE is reported during a phone call visit, an unscheduled onsite visit may be required to follow-up, per investigator.
- 18. Informed consent may be obtained from the parent(s) or legal guardian(s) up to 28 days prior to randomization. Consent can occur outside the screening visit or on the same day as the screening visit, but must occur prior to the screening visit.

Regeneron Pharmaceuticals, Inc.

Table 3: Part B: Unscheduled Visit for Potential Respiratory Illness - All Dose Regimens

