## 6.2.2.5. Visit 5 (Day 85±5 Days)

The following information will be collected, and the following procedures and assessments will be conducted:

- Concomitant medications and procedures
- Vital signs taken when the child is calm (including temperature, blood pressure, pulse, and respiration rate)
- Physical examination (including weight)
- AEs
- Blood sampling
  - Hematology (subjects with blood collection Schedule K only)
  - Blood chemistry (subjects with blood collection Schedule K only)
  - PK sampling (subjects with blood collection Schedule K only)
  - ADA sampling (subjects with blood collection Schedule K only)
- Pharmacoeconomic information on subjects who have experienced a medically attended respiratory event since last visit

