# 8.5. Antidrug Antibody Variables

Antidrug antibody variables include status (positive or negative) and titer as follows:

- Total ADA-positive subjects at any time
- Pre-existing immune reactivity defined as either an ADA positive response at baseline with all posttreatment ADA results negative, or a positive response at baseline with all posttreatment ADA responses less than 4-fold over baseline titer levels
- Treatment-emergent defined as either an ADA positive response after treatment when baseline results are negative, or if any posttreatment ADA-positive response is greater than or equal to 4-fold over baseline titer levels. The treatment-emergent responses will be further characterized into Persistent and Transient.
  - Persistent Response treatment-emergent ADA positive response with two or more ADA-positive sampling time points during the treatment period (and follow-up phase if any) such that the first and last ADA-positive sample (with no ADA-negative samples in between) is separated by at least a 12-week period or only the last collected sample is ADA-positive.
  - Transient Response Any treatment-emergent ADA-positive response that is not considered persistent
- Titer values
- Titer category
  - Low (titer < 1000)
  - Moderate (1000  $\leq$  titer  $\leq$  10 000)
  - High (titer >10 000)

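### The ADA persistence rule labels Schedule J and K infants positive at both post-baseline samples as transient, and the protocol and SAP classify a last-sample-only positive differently

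*SAP*

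**What the plan says.** SAP 4.8.2 divides treatment-emergent ADA (any post-baseline positive when baseline is negative or missing) into three classes:

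- The first asks for a sustained run: "persistent - defined as consecutive positive responses over at least a 12-week period".
- The second is for a final positive with none before it: "indeterminate - defined as positive only at the last sample analyzed".
- The third takes whatever is left over: "transient - defined as not persistent or indeterminate".

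Protocol 8.5 has only two classes. Its persistent class covers an unbroken run of positives whose first and last members are 12 weeks apart, and also a positive at the final sample alone: the response qualifies if the pair "is separated by at least a 12-week period or only the last collected sample is ADA-positive". Everything else treatment-emergent is transient.

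Planned ADA sampling in Part B is in Protocol Table 2 (Section 6.1), footnotes 10 to 14, and is repeated in SAP Appendix 11.2. Each infant is assigned one of five schedules:

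- M: screening, Day 29 and Day 150 or early termination.
- L: "ADA samples at screening, Day 57 (predose), and Day 150/ET".
- K: "ADA samples at screening, Day 85, and Day 150/ET".
- J: "ADA samples at screening, Day 113, and Day 150/ET".
- I: screening and Day 150 or early termination only.

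SAP 5.9.2 commits to evaluating persistent ADA.

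**The concern.** A reader takes *transient* to mean that the antibody response went away. Under a leftover definition it means only that the response failed two other tests. Where the sampling schedule cannot span 12 weeks, an infant can be positive at every post-baseline sample, including the last, and still be called transient.

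The ordering is also perverse. An infant positive only at Day 150 is *indeterminate* in the SAP, which leaves the question open. An infant on J or K with that same Day 150 positive plus an earlier one gets the more reassuring label. Under the protocol the contrast is sharper: a single positive at Day 150 is *persistent*, while positives at Days 113 and 150 are *transient*.

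Immunogenicity is a secondary objective of Part B (Protocol 2.2, SAP 1.2.2). Protocol 1.3 already uses the word transient in its benefit/risk account of the adult ADA findings. If it is used again for the infants, it should not cover children never shown to revert to negative.

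**Working it through.** **Inputs.** The threshold is 12 weeks × 7 = 84 days. Visit windows are in Protocol 6.2.2.3 to 6.2.2.7: Day 29±2, Day 57±2, "Visit 5 (Day 85±5 Days"), Day 113±5 and Day 150±5. The last planned sample therefore falls between Day 145 and Day 155.

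**Gap between the two planned post-baseline samples.** For a first sample at day d with window ±w:

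- nominal gap = 150 − d
- minimum gap = 145 − (d + w)
- maximum gap = 155 − (d − w)

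| Schedule | First sample | Nominal | Minimum | Maximum | Reaches 84? |
|---|---|---|---|---|---|
| M | 29±2 | 121 | 145 − 31 = 114 | 155 − 27 = 128 | always |
| L | 57±2 | 93 | 145 − 59 = 86 | 155 − 55 = 100 | always |
| K | 85±5 | 65 | 145 − 90 = 55 | 155 − 80 = 75 | never |
| J | 113±5 | 37 | 145 − 118 = 27 | 155 − 108 = 47 | never |
| I | none | – | – | – | one sample only |

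**Labels that result** (baseline ADA negative or missing, in-window planned samples):

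| Pattern | Schedules | SAP 4.8.2 | Protocol 8.5 |
|---|---|---|---|
| Positive at both | L, M | persistent | persistent |
| Positive at both | J, K | transient | transient |
| First only | J, K, L, M | transient | transient |
| Last only | I, J, K, L, M | indeterminate | persistent |

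The second row is the mislabelling. The fourth row is the disagreement between the documents; it covers every treatment-emergent positive on Schedule I.

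**After the second dose.** The earliest in-window planned sample after dose 2 is Day 80 and the latest is Day 155, a span of 155 − 80 = 75 days, below 84. The first post-baseline samples in L (Day 57 predose) and M (Day 29) both precede dose 2. ADA that first appears after dose 2 therefore cannot be classed persistent from planned samples.

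**Departures from plan.**

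- With early termination, L at nominal Day 57 needs a last sample on or after Day 57 + 84 = 141, and M at nominal Day 29 on or after Day 29 + 84 = 113.
- At the extremes of the wider analysis windows in SAP Appendix 11.3, K could reach 164 − 72 = 92 days, J at most 164 − 100 = 64, and L could fall to 133 − 71 = 62.
- Unscheduled ADA samples for suspected hypersensitivity (Protocol 6.2.4) could also change a label.

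**How many infants.** The documents give neither an infant ADA rate nor the share of infants on each schedule, so this is illustrative. The first-in-human study had 2 adults with treatment-emergent ADA (Protocol 1.1) and 110 exposed to REGN2222 (Protocol 1.2.2.1). Assume that both were exposed, that infants behave alike, and that the five schedules are equally filled:

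- rate: 2/110 = 1.8%, exact 95% CI 0.2% to 6.4%
- infants on REGN2222: 1200 × 2/3 = 800
- treatment-emergent: 800 × 0.0182 = 14.5 (1.8 to 51.3)
- on J or K: 14.5 × 0.4 = 5.8 (0.7 to 20.5)

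Under those assumptions, about 6 (1 to 21) is an upper bound on double-positives in J and K, because not every treatment-emergent infant there will be positive twice.

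**The case against.** The strongest reply is that this is a labelling matter of little consequence. SAP 5.9.2 names persistent ADA for evaluation and no transient analysis. Protocol 9.5.5.2 groups ADA prevalence by arm and titer level, not by persistence. Listings of positivity and titer by subject and time point are planned, so each double-positive will be visible. The leftover class adds no false persistent cases. All of that stands, and it limits the weight of the point. It does not make the label right.

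The inability to show persistence after dose 2 comes from sparse sampling, which Protocol 3.1.2.3 justifies by the need to limit blood draws. That also stands. Rewording cannot create persistence data; it only stops those infants being called transient. In the single-dose arm dose 2 is placebo, so there the Day 29 and Day 57 samples do follow the only active dose.

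The count rests on adults given other doses and routes, and on an allocation the documents do not state. It also leaves out placebo infants, whom SAP 3.4 includes in the ADA analysis set. The true number could be zero or above the range. The link to Protocol 1.3 is only suggestive: it describes a different study, and no definition of transient is given there.

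Moving a last-only positive from persistent to indeterminate can be defended as the more cautious choice. But the SAP does not explain the change. SAP 1.2.3 reports no modifications from the protocol's statistical section; because the ADA classes sit in Section 8.5, the change is an unexplained divergence and not a direct contradiction of that statement.

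**Conclusion.** The concern holds. For planned, in-window samples in infants with negative or missing baseline ADA, every double-positive on Schedule J or K is labelled transient under both documents without a later negative sample, and every last-sample-only positive has a different label in each. Only L and M can yield persistent.

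The effect is confined to a descriptive split of treatment-emergent ADA. ADA presence, titer and all efficacy analyses are unaffected. The number of infants involved is probably small but cannot be derived from the documents. The point is worth correcting before database lock because the rule gives the more reassuring class to the infant with more evidence of ADA.

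**What to change.** Put one rule in SAP 4.8.2 and Protocol 8.5:

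- **Persistent:** consecutive positives spanning at least 84 days.
- **Indeterminate:** last post-baseline sample positive, but the consecutive positives span less than 84 days. This includes a single positive at the last sample.
- **Transient:** last post-baseline sample negative and the 84-day rule not met.

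Report the persistent rate among infants whose first and last post-baseline ADA samples are at least 84 days apart, using actual sample dates. That settles eligibility for early terminators, out-of-window visits and unscheduled samples without special cases. State alongside it that planned samples after dose 2 span at most 75 days, so persistence of ADA first arising after dose 2 cannot be assessed.

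The cost is wording in two sections and a change to one derivation, with no new samples. There are two downsides. The persistent rate has a smaller denominator: Schedules I, J and (in-window) K drop out, as do infants who leave early. The indeterminate class also grows and mixes single last positives with short double-positive runs; the planned subject listings keep that distinction visible.
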